Avenir Muller Hip Stem Post-Market Surveillance Study

A multi-center, non-comparative, retrospective post-market surveillance study

PROTOCOL No. 09H08

NCT NUMBER: NCT04079127

PROTOCOL VERSION:
2009-10-06 - REV. 0

STUDY SPONSOR

**ZIMMER GMBH
[name]
P.O. BOX
[name]
SWITZERLAND**

Title:	A multi-centre, non-comparative, retrospective post-market surveillance study to obtain clinical outcomes data on the Zimmer Avenir Müller Hip Stem.
Sponsor:	Zimmer GmbH
Objectives:	The objective of this study is to obtain outcome data on the Avenir Müller Hip Stem by analysis of adverse events records, standard scoring systems, and radiographs. Data will be used to monitor survival, pain and mobility and to confirm safety and efficacy of the Avenir Müller Hip Stem.
Indication/ Target Population:	Patients suffering from severe hip pain and disability requiring a total hip arthroplasty.
Study Design:	Multi-centre, non-comparative, retrospective.
Clinical Phase:	Post-market
Number of Subjects:	A total of 150 patients will be enrolled in a multi-centre setting within Europe.
Length of Study:	Prospectively collected pre and peri-operative baseline data available. Follow-up visits at 3, 5 (optional), 7 and 10 years post-operatively.
Study Device:	Avenir Müller Hip Stem
Comparator Device/ Procedure:	None
Clinical Assessments:	Evaluations will be made using the Harris Hip Score (and/or PMA), and radiographically.
Safety Assessments:	Safety will be assessed by appropriate recording and reporting of adverse events throughout the study. All system components are CE marked and commercially available.
Statistical analysis:	Data collected will be summarized and reported to each participating Investigator. Statistical analysis is conducted by Zimmer or its designee.

General Statistical Method:

Data collected in the study will be summarized. Descriptive summaries will be the basis of study reports to participants.

Summaries will routinely describe categorical data as counts and percentages, and describe continuous data in the form of means, medians, standard deviations, minima, and maxima. Summaries of variables such as implant survival, return to function or time to event will generally be described via the Kaplan-Meier method and will be accompanied with the corresponding rates (expressed as percentages). Complication data will be summarized in the form of frequencies and percentages. Summaries may be further generated for strata within the study population, such as males/females, body mass index or primary diagnosis.

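### Does the Kaplan-Meier summary of implant survival need a written rule for selecting the 150 patients and counting revisions before enrolment?

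*Combined protocol and SAP*

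**What the plan says.** The synopsis title describes a "multi-centre, non-comparative, retrospective" study. Under Number of Subjects, "A total of 150 patients will be enrolled in a multi-centre setting within Europe". Under Indication/ Target Population, the patients are "Patients suffering from severe hip pain and disability requiring a total hip arthroplasty", a definition that applies at the time of surgery. Length of Study adds: "Prospectively collected pre and peri-operative baseline data available. Follow-up visits at 3, 5 (optional), 7 and 10 years post-operatively".

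The Objectives name the data source as "analysis of adverse events records, standard scoring systems, and radiographs" and the purpose: "Data will be used to monitor survival, pain and mobility and to confirm safety and efficacy". The Safety Assessments row separately provides for recording adverse events while the study runs.

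The General Statistical Method says: "Summaries of variables such as implant survival, return to function or time to event will generally be described via the Kaplan-Meier method", with the matching percentages. It makes descriptive summaries the basis of the study reports. It gives no time origin, entry time, or rule for revisions before enrolment.

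**The concern.** Kaplan-Meier with the clock at surgery estimates survival from surgery only if patients enter whatever happened to their stem afterwards, or if late entry is allowed for. Here the study is retrospective, the baseline data already exist, and the first listed visit is three years after the operation. A reader may picture patients being recruited at or near that visit. Stems revised in the first three years could then be under-represented, and the reported percentage would be survival given an unrevised stem at entry, presented as survival from surgery.

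The percentage has no comparator to put it in context. Survival is listed first among the outcomes to be monitored, and the data are also meant to support a statement on safety and efficacy. A favourable selection effect would pass straight into that statement, and no confidence interval would show it.

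**Working it through.** The sample size of 150 comes with no derivation, so there is no figure in the plan to reproduce. The check has two parts: what the text supports, and how large the effect could be.

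**Two readings of the text**

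- *Cohort defined at surgery.* The population is defined by the indication for the operation. Baseline data were collected prospectively and are on file. Visits are timed from the operation. Adverse event records are named as a data source, in a different row from the recording of events during the study. If early revisions are taken from those records, the bias is zero.
- *Cohort defined at a later contact.* The word used is enrolled, and the first visit is at 3 years. Both are compatible with late entry. But no sentence puts entry at 3 years or excludes patients already revised. The 3-year visit is a follow-up time measured from surgery and is not an entry criterion.

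**Size, on assumed inputs**

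Let S be true 10-year survival, p the share of stems revised before their own entry, and r the chance that such a stem is enrolled relative to the others. Then

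apparent S(10) = S / [(1 - p) + r × p].

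With S = 0.95:

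| p | r = 0 | r = 0.5 | r = 1 | r = 2 |
|---|---|---|---|---|
| 1% | 0.95/0.99 = 0.960 (+1.0 points) | 0.95/0.995 = 0.955 (+0.5) | 0 | 0.95/1.01 = 0.941 (-0.9) |
| 2% | 0.95/0.98 = 0.969 (+1.9) | 0.95/0.99 = 0.960 (+1.0) | 0 | 0.95/1.02 = 0.931 (-1.9) |
| 3% | 0.95/0.97 = 0.979 (+2.9) | 0.95/0.985 = 0.964 (+1.4) | 0 | 0.95/1.03 = 0.922 (-2.8) |
| 5% | 0.95/0.95 = 1.000 (+5.0) | 0.95/0.975 = 0.974 (+2.4) | 0 | 0.95/1.05 = 0.905 (-4.5) |

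The +5.0 entry is degenerate: it needs every 10-year revision to fall before entry. The documents do not fix the sign, because nothing in them sets r.

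The worst form of late entry enrols only stems unrevised at 3 years. The estimate is then S(10)/S(3). If 30% to 70% of the 10-year revisions fall before year 3:

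- S = 0.97: from 0.97/0.991 = 0.979 (+0.9) to 0.97/0.979 = 0.991 (+2.1)
- S = 0.95: from 0.95/0.985 = 0.964 (+1.4) to 0.95/0.965 = 0.984 (+3.4)
- S = 0.90: from 0.90/0.97 = 0.928 (+2.8) to 0.90/0.93 = 0.968 (+6.8)

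**Staggered entry**

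Suppose entry is uniform over 0 to 3 years and revisions are spread evenly over that time. If 1% are revised by year 3, about half of them, 0.5%, are revised before their own entry. Ordinary Kaplan-Meier then gives 0.95/0.995 = 0.955. With 3% revised by year 3 it gives 0.95/0.985 = 0.964. Delayed-entry Kaplan-Meier returns 0.950 in both cases in a large simulation, so this form can be corrected at analysis from entry dates.

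That correction is fragile at this size. At 0.1 year about 150 × 0.1/3 = 5 patients are at risk, and one revision then multiplies the curve by 4/5, a drop of about 20 points.

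**Scale**

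With 150 patients and no censoring, the 95% half-width at S = 0.95 is 1.96 × √(0.95 × 0.05/150) = 0.035, or 3.5 points. At S = 0.90 it is 4.8 points. Most of the shifts above are smaller than the half-width for the same S. The 5% cases with r = 0 or r = 2, and the heaviest early-revision case at S = 0.90, are larger.

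**The case for a change.** The strongest case for a change is that selection bias is systematic. It does not shrink with more patients, and comparing it with a sampling half-width does not excuse it. Prospectively collected baseline data do not prove that everyone with such data is later enrolled, so the harmless reading is an inference. If every patient entered at 3 years, no survival method could recover the earlier period, since delayed-entry Kaplan-Meier would also return the conditional figure. Adding a sentence to the protocol costs little.

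Part of this stands. The three rules are absent, and if entry really were at a later contact the percentage would have to be labelled as conditional on an unrevised stem at entry.

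The rest does not carry the point. The argument shows what would follow from a selection rule that the text nowhere states; it does not show that the stated plan gives a wrong answer. The claim that nothing can be done afterwards holds only where nobody is observed early. With staggered entry, entry dates allow a correction, although an unstable one with 150 patients. Nor is the remedy only a sentence: tracing the revision status of every consecutive implantation at each centre is real work where records are incomplete.

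**Conclusion.** This is missing detail in a synopsis-level text, not a demonstrated bias. The wording is compatible with, and leans towards, a record-based cohort with the clock at surgery, for which the bias is zero. The alternative needs an entry rule that is not in the documents. With an assumed true 10-year survival of 95% and 1% to 5% revised before entry, the effect runs from -4.5 to +5.0 points. Under the extreme case of entry only for stems unrevised at 3 years, with assumed survival of 90% to 97%, it runs from +0.9 to +6.8 points. None of these inputs comes from the plan.

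No test, comparison or threshold depends on the survival percentage, and scores, radiographs and complication frequencies are reported beside it. A competent analyst would take surgery as time zero, count revisions found in existing records, and state in the report how many implanted patients were enrolled and on what basis. That settles the meaning of the percentage without amending the plan. The conclusion would change if a document showed that stems revised before enrolment were excluded.

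### Complications get only counts and percentages over up to 10 years of unequal follow-up; read as a 10-year risk over all enrolled, the percentage would be modestly too low

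*Combined protocol and SAP*

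**What the plan says.** The complication analysis is one sentence under General Statistical Method: "Complication data will be summarized in the form of frequencies and percentages". The sentence before it treats other outcomes differently: "Summaries of variables such as implant survival, return to function or time to event will generally be described via the Kaplan-Meier method". Its wording is open enough to permit a time-to-complication summary, but it does not name complications or commit to one.

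Elsewhere in the synopsis:

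- Length of Study: "Follow-up visits at 3, 5 (optional), 7 and 10 years post-operatively".
- Number of Subjects: "A total of 150 patients will be enrolled in a multi-centre setting within Europe".
- Safety Assessments: "Safety will be assessed by appropriate recording and reporting of adverse events throughout the study". This sets a collection period, but not the denominator or time window of a percentage.
- Objectives: outcome data are obtained "by analysis of adverse events records, standard scoring systems, and radiographs", and are meant "to confirm safety and efficacy of the Avenir Müller Hip Stem".

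Neither document states an expected death, loss or complication rate, or when patients are enrolled relative to surgery.

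**The concern.** Over a decade some patients will die and others will be lost, so follow-up will be unequal. A percentage over everyone enrolled treats a patient lost at year 3 without a complication as event-free to year 10. Unless later events still reach the adverse event records, the percentage then falls below the 10-year risk, and by more at later visits and with more loss. Reports at different years, or for strata with different loss, would not be directly comparable.

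The study has no comparator, so the absolute complication figure is itself the safety result. The plan already handles censoring for implant survival; the gap mainly concerns complications that do not end in implant failure.

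**Working it through.** The plan has no figure to reproduce: 150 is given without a target precision, expected risk or expected loss. The check therefore asks how far an all-enrolled percentage would fall below the cumulative incidence with death as a competing event.

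**Inputs.** From the documents: N = 150; visit years 3, 5, 7 and 10. Assumed: net 10-year complication risk 10%; 25% dead and 25% lost by year 10, each as a net probability; independent, constant hazards.

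**Hazards per year.**

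- Complication: a = −ln(0.90)/10 = 0.01054
- Death: d = −ln(0.75)/10 = 0.02877
- Loss: c = −ln(0.75)/10 = 0.02877

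**Formulas at time t, loss starting at surgery.**

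- Cumulative incidence = a/(a+d) × [1 − exp(−t(a+d))]
- All-enrolled percentage = a/(a+d+c) × [1 − exp(−t(a+d+c))]
- Expected number at risk = 150 × exp(−t(a+d+c))

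| Year | Cumulative incidence | All enrolled | Relative shortfall | At risk |
|---|---|---|---|---|
| 3 | 2.98% | 2.86% | 4.1% | 122 |
| 5 | 4.78% | 4.47% | 6.6% | 107 |
| 7 | 6.45% | 5.87% | 9.0% | 93 |
| 10 | 8.71% | 7.64% | 12.3% | 76 |

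At year 10 the gap is 8.71 − 7.64 = 1.07 points, or 1.6 of 150 patients.

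**Deaths alone.** Setting c = 0 makes the two formulas identical (8.71% each). The shortfall comes from living patients who are lost, not from deaths.

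**Entry after surgery.** The design is retrospective. If patients enter at about year 3 (an assumption), none of the enrolled can be lost before then. Put the same 25% loss into years 3 to 10, with c = −ln(0.75)/7 = 0.04110 after year 3 and zero before, and leave complications and deaths running from surgery. The shortfall at years 3, 5, 7 and 10 becomes 0%, 1.5%, 4.1% and 8.2%; the last is 1.1 patients.

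**Timing of complications and amount of loss.** Relative shortfall at year 10, loss from surgery:

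| Complication hazard | 15% loss | 25% loss | 35% loss |
|---|---|---|---|
| Constant | 7% | 12% | 18% |
| 80% in year 1 | 2% | 4% | 5% |
| 80% after year 5 | 10% | 16% | 23% |

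**Against sampling error.** With no censoring, the 95% half-width at 8.71% would be 1.96 × √(0.0871 × 0.9129/150) = 4.5 points. Simulating 4,000 studies under constant hazards gives 4.6, 4.8 and 5.0 points at 15%, 25% and 35% loss, against all-enrolled errors of 0.6, 1.1 and 1.5 points. The largest gap in the table above (80% after year 5, 35% loss) is 8.33 − 6.41 = 1.9 points, also well inside. A Wilson interval on the all-enrolled percentage covers the true cumulative incidence 93.5% of the time in the base case and 91.4% at 35% loss with constant hazards.

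**The case against.** The strongest reply is that the plan never chooses the all-enrolled denominator and never says the percentage is a 10-year risk. Its reports are descriptive, no complication threshold or test is planned, and a count of observed complications is correct as it stands. This stands, and it makes the concern conditional.

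Second, implant survival is already analysed with censoring, and the open wording of that sentence could take in time to complication. This stands in part: what is permitted is not committed to.

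Third, a missed visit need not mean a missed event, because adverse event records are a named source. This also stands: the shortfall arises only for patients lost before any complication whose later events are not captured.

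Fourth, the error is small, and modelling loss from surgery may not suit a retrospective study. Both are right, and the second lowers the 10-year figure from about 12% to about 8%.

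A reader might go further and infer that the plan will understate complication risk, or that the same data could be reported anywhere across a wide range. Under the base-case assumptions, events over patients with an event or complete follow-up would give 0.0764/(0.0764 + 0.90 × 0.75 × 0.75) = 13.1%, for example. The documents do not support either reading. All enrolled is only one interpretation of an undefined percentage, and nothing in the text points to the event-or-complete denominator.

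**Conclusion.** The point holds in a limited, conditional form. If the percentage is taken over all enrolled and read as a 10-year risk, it is biased downward, and the bias grows with time and loss. Under the assumed 10% net risk, 25% deaths and 25% loss, the 10-year relative shortfall is about 12% with loss from surgery and about 8% with entry at about year 3. It is 2% to 5% across 15% to 35% loss from surgery if most complications are early, and larger (10% to 23%) only if most are late. Every one of these gaps is smaller than the sampling error of a 150-patient study. All rates are assumptions; the documents fix the direction but not the size.

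The missing denominator and period are on their own only missing detail. The substantive gain is a censoring-aware summary beside the counts, in line with what the plan already does for implant survival. Priority: minor.

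**What to change.** Keep the counts and percentages, and state the denominator and the period for each.

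For complications with a known onset date, add the cumulative incidence at years 3, 7 and 10 (and 5 where available), with:

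- death as a competing event;
- loss censored at last contact;
- delayed entry accounted for if patients are enrolled after surgery;
- a 95% confidence interval and the number at risk.

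Where only the visit interval is known, say so and report counts by interval over the patients assessed.

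Stating the denominator and period needs no new data. The rest costs slightly more analysis work and relies on onset dates that the documents do not confirm. Intervals at 10 years will be wide: in the base case about 76 of 150 are still at risk, with about 11 observed events in total (150 × 0.0764 = 11.5), so figures by complication type will be imprecise. The results will look slightly less favourable than an all-enrolled percentage.
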